8.4.5 Suspected Unexpected Serious Adverse Reactions

Any AE that is serious, associated with the use of the study intervention, and unexpected (suspected unexpected serious adverse reaction [SUSAR]) has additional reporting requirements, as described below.

- If the SUSAR is fatal or life-threatening, associated with study intervention, and unexpected, regulatory authorities and IEC/IRB will be notified within 7 calendar days after the Sponsor learns of the event. Additional follow-up (cause of death, autopsy report, and hospital report) information should be reported within an additional 8 days (15 days total).
- If the SUSAR is not fatal or life-threatening but is otherwise serious, associated with study intervention, and unexpected, regulatory authorities and IEC/IRB will be notified within 15 calendar days after the Sponsor learns of the event.

The Sponsor's designated safety services will also provide periodic and annual safety updates to the regulatory authorities, IEC/IRB responsible for the study, and investigators as per local regulations. These updates will include information on SUSARs and other relevant safety findings.

8.4.6 Abnormal Laboratory Values/Vital Signs/Electrocardiograms

Laboratory/vital signs/ECG abnormalities should be reported as an AE/SAE if any one of the following criteria is met:

- Result is associated with signs/symptoms.
- Requires additional diagnostic testing and/or interventions.
- Leads to a change in dose, discontinuation of or interruption to the study drug.

Repeats of an abnormal test result without any of the above criteria do not constitute an AE.

Any test result determined to be an error is not required to be reported as an AE.

8.4.7 Method of Detecting AEs and SAEs

Care will be taken not to introduce bias when detecting AEs and/or SAEs. Open-ended and nonleading verbal questioning of the subject is the preferred method to inquire about AE occurrence.

8.4.8 Follow-up of AEs and SAEs

After the initial AE/SAE report, the Investigator is required to proactively follow each subject at subsequent visits/contacts. All SAEs will be followed until resolution, stabilisation, until the event is otherwise explained, or the subject is lost to follow-up (as defined in Section 7.3).

The Investigator is obligated to perform or arrange for the conduct of supplemental measurements and/or evaluations as medically indicated or as requested by the Sponsor to elucidate the nature and/or causality of the AE or SAE as fully as possible. This may include additional laboratory tests or investigations, histopathological examinations, or consultation with other health care professionals. If subject dies during participation in the study or during a recognized follow-up period, the Investigator will provide the Sponsor with a copy of any post-mortem findings including histopathology.

New or updated information will be recorded in the originally completed eCRF within 24 hours of receipt of the information.

8.4.9 Regulatory Reporting Requirements for Serious Adverse Events

Investigators and other study site personnel must inform the Sponsor's designated safety services of any SAE that occurs (whether or not attributable to the study drug) in the course of the study within one day (i.e., immediately but no later than 24 hours or as per local regulation) of when he or she becomes aware of it.

Follow-up information on SAEs must also be reported to Sponsor's designated safety services by the Investigator within 24 hours or as per local regulation.

If a non-serious AE becomes serious, this and other relevant follow-up information must also be provided to the Sponsor's designated safety services within 24 hours or as per local regulation as described above.

All SAEs and pregnancies will be recorded in the eCRF. As soon as the SAE/pregnancy is recorded in the eCRF, a notification alert will be sent to the Sponsor's designated safety services. A notification email of the event describing it in the e-mail text is not sufficient. Whenever required applicable local SAE reporting Form will be used (e.g., Appendix XI in India), in addition to eCRF update.

Source documents relevant for the SAE should only be reported upon request by Sponsor's designated safety services. Due to data protection laws, please ensure redaction of the subject's identifiers (name, address, and date of birth [only year of birth is allowed]) from the discharge summary, autopsy report, laboratory reports, and any other documents/reports when sending to the Sponsor's designated safety services.

There may be situations when an SAE has occurred, and the Investigator has minimal information to include in the initial SAE report. However, it is very important that the Investigator always makes an assessment of causality for every event prior to transmission of the SAE report form.

Minimum criteria are identifiable subject (number), a suspect product (i.e., study drug or concomitant medication), an identifiable reporting source (Investigator/study site identification), and an event or outcome that can be identified as serious. The Investigator may change his/her opinion of causality in the light of follow-up information, amending the eCRF SAE page accordingly. The causality assessment is one of the criteria used when determining regulatory reporting requirements for SAEs.

When an SAE is discovered by the study site or is identified by a designated clinical research associate during study site visits, SAEs will be entered by the study site members into the eCRF, which contains specific questions for events regarded as serious. Designated personnel will receive the alert through automated e-mail notification.

The Sponsor/designee representative will work with the Investigator to compile all the necessary information and ensure that the appropriate Sponsor/designee representative receives a report within 24 hours for all SAEs.

The Sponsor/designee will bear responsibility of expedited and periodic reporting to the health authorities according to national requirements. The Investigator must comply with any applicable site-specific requirements related to the reporting of SAEs (particularly deaths and SUSARs) to the IEC/IRB that approved the study.

CCI

8.4.10 Pregnancy

Pregnancy itself is not regarded as an AE unless there is a suspicion that the study drug may have interfered with the effectiveness of a contraceptive medication. If a pregnancy is reported for a subject, no further study drug will be administered to this subject and the outcome of all pregnancies (spontaneous miscarriage, elective termination, normal birth or congenital abnormality) must be followed up and documented in the eCRF. Follow-up should be performed up to delivery, after the examination of the newborn, and until 12 weeks of age, when follow-up information regarding the pregnancy and the outcome of the newborn should be entered in the eCRF.

All congenital abnormalities/birth defects should be classified as SAEs. Spontaneous miscarriages should also be reported and handled as SAEs. Elective abortions without complications should not be handled as SAEs but should be reported as an AE. All outcomes of pregnancy must be reported to the Sponsor's designated safety services via the eCRF.

Pregnancy outcomes must be collected for the female partners of any males who took study drug in this study. Consent to report information regarding these pregnancy outcomes should be obtained from the female partner.

Pregnancies must be reported to the Sponsor's designated safety services using the reporting details provided in Section 8.4.2 within 24 hours of awareness.

8.4.11 Death Events

Should a death occur within the study period or within 16 weeks after the last administration of study drug an AE form and an SAE form should be completed, detailing the AE that resulted in the death (Note, death is an outcome, not an event). The SAE must be reported to the Sponsor or Sponsor's designated safety services within 24 hours as described in Section 8.4.2. The report should contain a comment regarding the co-involvement of progression of disease, if appropriate, and should assign main and contributory causes of death. However, death due to disease progression to be reported as SAE from sites in India.

8.5 Study Conduct During the COVID-19 Pandemic

COVID-19 is a viral illness caused by the novel coronavirus (also called SARS-CoV-2) and has impacted most of the countries across the globe. It was declared as a global public health emergency by the WHO on 30 Jan 2020, and was declared as a pandemic on 11 Mar 2020. This pandemic has impacted the conduct of clinical trials in various ways.

8.5.1 Contingency Measures Implemented During the COVID-19 Pandemic

In the current global outbreak of COVID-19, [name] s Laboratories (DRL) has recognized the potential impact on the conduct of RI-01-006 study due to various reasons. Considering that the safety of study participant is paramount, DRL has initiated various contingency measures for the well-being of subjects and in order to ensure compliance with guidance issued by various regulatory agencies:^{24,25}

- COVID-19 protective measures: Recommendation to study sites to inform and encourage all study subjects to practice COVID-19 basic protective measures at all times.
- COVID-19 testing and COVID-19 related screening questionnaire:

- a. Each subject being randomized will undergo COVID-19 testing (preferably RT-PCR) and only subjects with confirmed negative test results will be administered the study drug. Additional testing for COVID-19 during the course of study may be performed at the discretion of the Investigator. All such test results will be documented appropriately in CRF.
- b. COVID-19 related screening questionnaire to rule out active COVID-19 infection as well as to evaluate further if potential study subjects are at risk of acquiring COVID-19 at screening visit and during the study period. Study drug will be administered only in those subjects who are considered at no-risk by the Investigator based on this evaluation.
- Inform Consent Document (ICD) amended to include possible risks related to COVID-19 and rituximab treatment. All ongoing subjects will undergo re-consent with a newer version of the ICD, after approval from a respective ethics committee (EC). All new subjects being screened will be asked to give their consent using the newer version of the ICD.
- Advise study sites to prioritize subjects' safety and priority care in the event of COVID-19 infection.
- The Investigator must stop rituximab treatment if any of the study subjects acquire COVID-19 infection while in the study. Re-institution of therapy should be done after careful benefit risk assessment by the Investigator once the subject has been confirmed as cured of COVID-19 with appropriate laboratory testing.
- The Investigator is encouraged to do telephonic inquiry of study subjects to know about their overall well-being, adverse events, including suspected COVID-19 symptoms, concomitant medications etc.
- COVID-19 events in the study are to be considered as "Events of Special Interest (EOSI)" and all relevant detailed information will be collected, such as diagnosis, management and outcome. All events related to or linked to COVID-19 and meeting SAE criteria must be reported as an SAE.

All details of remote monitoring, including discussion with sites on informed consent process, subject eligibility, review of central lab data, review of data entry, query resolution, pending actions, review of protocol deviations etc., have been captured in the monitoring plan, as applicable.

Detailed information about the type of data to be collected, handling of missing data or assessments/procedures will be captured in the eCRF filling guidelines/data management plan, if required. Listings/summaries of all subjects affected due to COVID-19, including protocol

deviations and additional safety contingency measures will be generated based on the available data, if required. Corresponding details will be mentioned in the SAP.

Based on the evolving COVID-19 pandemic, the Sponsor will revisit these contingency measures for any further changes, or for their continuation/discontinuation, as needed, while ensuring subject safety and trial data integrity throughout the conduct of the study.

8.6 Treatment of Overdose

A drug overdose is defined as the accidental or intentional use of a drug or medicine in an amount that is higher than the protocol-specified dose. Rounding off is unavoidable in the preparation of rituximab infusion solutions. Due to this reason, excess

CCI for the subject will not be considered an overdose. Every overdose must be reported to the Sponsor's designated safety services within 24 hours of awareness as described in Section 8.4.2, irrespective of whether the overdose was associated with an AE/SAE. Subjects who experience overdose should be closely monitored.

9 Statistical Considerations

9.1 Statistical Hypotheses

9.1.1 General Principles

All individual data as well as results of statistical analyses, whether explicitly discussed in the following sections or not, will be presented in individual subject data listings and statistical summary tables.

In general, continuous variables will be summarised using the following standard descriptive summary statistics: number of observations, arithmetic mean, standard deviation, minimum, median, and maximum. Categorical variables will be displayed by means of frequency tables including percentages.

An additional analysis may be performed based on country specific requests/ requirements by the relevant authorities.

An SAP will be prepared and finalised before the study data are unblinded.

The statistical analysis will be performed using SAS[®] version 9.4 or higher.

9.1.2 Missing Data

Imputation of missing data in the primary efficacy analysis is described in Section 9.4.1.1 Partial dates for start or stop date of AEs will be imputed in an appropriately conservative way. Detailed methods for handling missing data will be given in the SAP. For substantial missing assessments due to the COVID-19 pandemic additional sensitivity analyses will be performed to determine if there was an impact on the efficacy endpoints. Methods for handling missing data should outline the assumptions utilized and discuss if this method of choice may have an effect on the estimate of the treatment effect.

Other missing values will not be imputed, unless otherwise specified in each analysis section.

9.1.3 Inter-current events due to COVID-19

Handling (i.e., analysis and presentation) of intercurrent events and data/visit impacted due to COVID-19 pandemic will be described in the SAP.

The following events are considered as intercurrent events due to COVID-19 pandemic and any study data missing as an outcome of these events will be handled as missing data impacted due to COVID-19:

- COVID-19 infection or death due to COVID-19 (as an Event of Special Interest)
- Protocol deviation including missing assessment due to COVID-19 pandemic
- Any other documented event which may interfere the study conduct and is reasonable related to COVID-19 pandemic

Full details of the COVID-19 related intercurrent events definitions will be provided in SAP.

9.1.4 Demographic and Baseline Characteristics

Demographic and baseline characteristics will be analysed in a descriptive fashion and results will be presented overall and by treatment group.

9.1.5 Subject Disposition

The following will be summarised (overall and by treatment group where applicable):

- Subjects screened
- Subjects randomised
- Subjects treated
- Subjects in each analysis population
- Subjects completing the study/withdrawing early (including withdrawal reason)
- Subject allocation by study site

9.2 Sample Size Determination

Published data for rituximab treatment versus a "watch and wait" strategy in the first line treatment of LTBFL (Ardeshna et al. 2014) revealed

CCI

CCI	
	CCI

Based on the observed pooled best overall response (BOR) rate, up to week 28, the revised total sample size obtained in the BSSR is 312 subjects (156 per group) to be recruited.

9.3 Populations for Analyses

9.3.1 Intent to Treat Population

The Intent to Treat (ITT) Population will include all randomised subjects. The primary efficacy analysis will be based on the ITT Population.

9.3.2 Per Protocol Population

The PP Population will include all subjects who are randomised into the study, receive at least one dose of study drug (sufficient compliance to be evaluated under blind conditions), have measurable disease at Baseline as confirmed by central review, have an at least one available valid response evaluation up to 7 months (\pm 4 weeks), and no major protocol deviations (such as administration of a forbidden treatment) that would significantly impact the primary efficacy endpoint. If the forbidden treatment was administered due to PD, the subject will be included in the PP Population as a non-responder. In the EMA analysis, both ITT and PP population will be considered as primary.

Subjects will be considered to have a valid response evaluation if all required tests in accordance with published response criteria¹³ are available and have been obtained within \pm 28 days of the scheduled date, and the central imaging reviewers consider all imaging at 3 months (Week 12) and 7 months (Week 28) as properly evaluable for size comparison with the baseline images, and subjects have not received forbidden medications or other treatments for LTB-FL.

Analysis of the PP Population may allow easier detection of any differences in treatment since the population includes only subjects who adhere to the protocol. Identification of the PP Population will be determined at one or several blinded data review meetings prior to unblinding.

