9.4.1 Efficacy Analyses

9.4.1.1 Analysis of Primary Efficacy Endpoint

The primary efficacy endpoint is the BORR i.e., the proportion of responders in each treatment arm who achieve a best overall response of either CR, CRu or PR up to Month 7 (Week 28) based on central radiology review in accordance with the response criteria for malignant lymphoma.¹³ Subjects who are included in the ITT Population but do not have efficacy assessments will be assessed as non-responders. The estimated difference (DRL_RI minus MabThera[®]) and its 95% CI will be obtained using the test -based exact binomial confidence interval method.^{27, 28} Equivalence will be concluded for FDA if the 90% CI and for EMA if the 95% CI of the BORR difference is completely contained within the pre-defined interval (-17%, 17%).

CCI . Full details

of the primary endpoint analysis including multiplicity considerations will be provided in the SAP.

Various sensitivity analyses will be conducted to confirm the robustness of the primary efficacy analysis result, including but not limited to:

• CCI

•	
	CCI
•	
	CCI
•	
	CCI

Additional details regarding sensitivity analyses for inter current events due to COVID-19 will be available in SAP.

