10.1.10 Protocol Approval and Amendment

Before the start of the study, the study protocol and/or other relevant documents will be approved by the IEC/IRB/Competent Authorities, in accordance with local legal requirements. The Sponsor must ensure that all ethical and legal requirements have been met before the first subject is enrolled in the study. In case of any changes implemented due to medical emergencies, the same needs to be promptly reported to the Sponsor and the IEC/IRB.

This protocol is to be followed exactly. To alter the protocol, amendments must be written, receive approval from the appropriate personnel, and receive IEC/IRB/Competent Authority approval prior to implementation (if appropriate). In the US: Following approval, the protocol amendment(s) will be submitted to the Investigational New Drug (IND) under which the study is being conducted.
Administrative changes (not affecting the subject benefit/risk ratio) may be made without the need for a formal amendment. All amendments will be distributed to all protocol recipients, with appropriate instructions.

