1 INTRODUCTION

[name] (DRL) is developing a proposed biosimilar version of the chimeric anti-CD20 monoclonal antibody (mAb), rituximab (DRL_RI). DRL_RI is a chimeric human/murine IgG1 kappa mAb consisting of murine light and heavy chain variable regions and human constant region sequences. The molecule is composed of two heavy chains of 451 amino acids each and two light chains of 213 amino acids each with a molecular weight of 145 kDa. Each of the heavy chains contains one N-linked glycan (resulting in 2 N-linked glycans per molecule).

This document describes planned statistical analyses as well as the rules and conventions to be used in the presentation of efficacy, safety, pharmacokinetics, pharmacodynamics, and immunogenicity data for [name] S.A.'s "Randomised, Double-blind, Parallel-group, Phase III Study to Compare the Efficacy, Safety, and Immunogenicity of Proposed Rituximab Biosimilar (DRL_RI) with MabThera[®] in Subjects with Previously Untreated, Stage II-IV, Cluster of Differentiation (CD)20 Positive, Low Tumour Burden Follicular Lymphoma".

This Statistical Analysis Plan (SAP) is applicable for unblinded statistical analysis of all data up to Week 28, and for the statistical analysis of all data up to Week 52 after database lock and general unblinding after the end of the study.

For the purposes of analysis, the study will be unblinded to specified Sponsor/designee members (refer to the latest version of Blinding Maintenance Plan (BMP)) – but not investigators or subjects – once all subjects have reached Week 28 (or earlier termination of study). All individuals with access to unblinded data and analysis results up to Week 28 will sign a confidentiality agreement to maintain the study blind up to general unblinding after final database lock. For the Week 28 CSR analysis, all data up to Week 28 (\pm 7 days, the allowed visit window for the Week 28 visit) will be included. Analysis for the Week 52 CSR will be prepared after database lock and general unblinding after study closure.

The analyses described in this SAP are based upon the following study documents:

- Clinical Study Protocol RI-01-006, version 5.0 (27 October 2021)
- Electronic Case Report Form (eCRF), Version 9.0 (21 March 2022).

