4.4 Analysis Sets

4.4.1 Intention-To-Treat Analysis Set

The Intention-To-Treat (ITT) Analysis Set will include all randomized subjects. The primary efficacy analysis will be based on the ITT Analysis Set.

If a subject received incorrect study drug, i.e., study drug different to the one assigned per the randomization list, the subject will be summarized and analyzed for the study treatment group per the randomization list. If a subject's stratum has been entered incorrectly in the randomization system, i.e., conflicting with the data in the clinical database, the stratum entered in the randomization system will be used for summaries and analyses.

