4.4.2 Per-Protocol Analysis Set

The Per-Protocol Analysis Set (PPS) will include all randomized subjects who

- received at least one dose of study drug (sufficient compliance as defined in Section 4.9)
- have measurable disease at Baseline as confirmed by central review
- have an at least one available valid response evaluation up to Week 28 (\pm 4 weeks)
- and no major protocol deviations (such as administration of a forbidden treatment) that would significantly impact the primary efficacy endpoint (if, however, the forbidden treatment was administered due to PD, the subject will be included in the PPS as a non-responder).

[name] S.A	
Protocol RI-01-006	

Subjects will be considered to have a valid response evaluation if all required tests in accordance with published response criteria¹³ are available and have been obtained within \pm 4 weeks of the scheduled date, and the central imaging reviewers consider all imaging at Week 12 and Week 28 as properly evaluable for size comparison with the baseline images, and subjects have not received forbidden medications or other treatments for LTB-FL.

Final composition of the PPS will be determined prior to unblinding.

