4.10.1.4 Multiple Comparisons/Multiplicity

No multiplicity adjustment is needed for this study as there is only one primary efficacy endpoint, no repeated analysis of the primary endpoint and each Health Authority will base the statistical analysis of the primary endpoint on either the FDA or EMA approach described in this SAP.

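### Protocol 9.3.2 makes ITT and per-protocol both primary for EMA; the visible SAP draws the EMA conclusion on ITT alone, files the per-protocol analysis as supplementary, and does not declare the change

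*Protocol*

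**What the plan says.** **Protocol.** Section 9.3.2, on the PP population, says "In the EMA analysis, both ITT and PP population will be considered as primary". Section 9.3.1 says "The primary efficacy analysis will be based on the ITT Population", with no split between regulators. The decision rule in 9.4.1.1 reads "Equivalence will be concluded for FDA if the 90% CI and for EMA if the 95% CI of the BORR difference is completely contained" within (-17%, 17%). Its visible text names ITT only for scoring subjects without efficacy assessments as non-responders, and it leaves multiplicity to the SAP.

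**SAP.** Section 1 gives protocol version 5.0 as its basis.
- Section 4.4.1: "The primary efficacy analysis will be based on the ITT Analysis Set".
- Section 4.10.2.1 runs the main analysis on ITT and states the EMA rule there, with no PPS condition.
- Section 4.4.2 closely follows the protocol's PP definition but omits the EMA sentence. It adds "Final composition of the PPS will be determined prior to unblinding".
- Section 4.10.2.3.2 repeats the exact-score and Mantel-Haenszel analyses on the PPS, under the supplementary analyses, whose stated purpose is robustness.
- Section 4.10.1.4 needs no multiplicity adjustment because "there is only one primary efficacy endpoint, no repeated analysis of the primary endpoint". It does not mention the PPS.
- Section 4.14 lists two changes: the model for the B-cell effect area, and more specific intercurrent events.

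**The concern.** One analysis cannot be both primary and supplementary for the same regulator. The protocol sentence does not look like a leftover: Amendment 4 revised that paragraph and kept it, and 9.3.2 gives a reason, that the PP population may show treatment differences more easily. Section 4.14 is where a reader would expect such a departure, and it records one as small as the B-cell model.

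What is at stake is the success criterion for one of two named regulators. If the role of the PPS result stays open until results are known, it can be settled according to which population passes.

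**Working it through.** **1. The texts side by side**

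| Question | Protocol | SAP |
|---|---|---|
| Primary population, general | ITT (9.3.1) | ITT (4.4.1) |
| Primary population, EMA | ITT and PP (9.3.2) | ITT (4.10.2.1) |
| Status of the PP analysis for EMA | primary (9.3.2) | supplementary (4.10.2.3.2) |
| How the two combine | not in visible text | not in visible text |
| Declared as a change | n/a | no (4.14) |

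If both sets must pass, no alpha adjustment is needed and the cost is power. If either could suffice, the reasoning in SAP 4.10.1.4 would not cover it. If PP has no decision role, protocol 9.3.2 is wrong.

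**2. The plan's own figure.** The 312 (156 per arm) in SAP 4.13.2 cannot be reproduced uniquely, because the pooled rate, assumed difference and dropout are not visible. With a normal approximation at 95% CI and 80% power, a 70% rate and no difference give (1.96 + 1.2816)² × 2 × 0.70 × 0.30 / 0.17² = 152.7, so 153 per arm and 306 in total. A 75% rate with -3 points gives 314. An 85% rate with -5 points and 10% dropout gives 310. Only the 156 per arm is used below.

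**3. How often ITT passes and PPS fails.** Assumed: both must pass; score tests at -0.17 and +0.17 with z = 1.96; 16, 23 or 31 excluded per arm (10, 15, 20%). The 88% is the only expected reference rate visible (SAP 4.10.2.3.4); 75% and 80% are assumed. With random exclusion:

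| Reference BORR | True difference | 10% | 15% | 20% |
|---|---|---|---|---|
| 75% | 0 | 7.0% | 9.9% | 13.7% |
| 80% | 0 | 4.8% | 7.1% | 10.1% |
| 88% | 0 | 1.2% | 1.9% | 3.0% |
| 75% | -3 points | 7.9% | 11.1% | 14.8% |
| 88% | -3 points | 3.4% | 4.8% | 7.0% |

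Exclusions need not be random. SAP 3.2.1.1 and 4.10.2.1 count subjects with no tumour evaluation as ITT non-responders, and the PPS definition removes those same subjects. Holding the ITT rate at 75% with no true difference:

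| Share of excluded who respond | 10% excluded | 20% excluded |
|---|---|---|
| random (75%) | 7.0% | 13.7% |
| half | 5.0% | 7.1% |
| a quarter | 3.0% | 2.0% |
| none | 0.4% | 0.0% |

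These rows fix the number excluded. If it varies by chance, a check run of 300,000 trials per scenario gives 2.2% and 0.1% in the last row. At 88% with 10% excluded, half of them responders, the figure is 0.1% (1.4% at -3 points).

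**4. One data set.** ITT 114/156 v 125/156 is -7.1 points; the exact one-sided p at -0.17 is 0.0197, below 0.025, so it passes. Remove 16 per arm, of whom 12 and 13 are responders: 102/140 v 112/140, also -7.1 points, p = 0.0271, fails. Remove 16 non-responders per arm instead: 114/140 v 125/140, p = 0.018, passes. With 4 responders among the 16 in each arm: 110/140 v 121/140, p = 0.0245, passes.

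**5. Power under a joint rule** (BORR 80%, -3 points, 10% excluded):

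| Excluded subjects | Joint | ITT alone, same model |
|---|---|---|
| random | 78% | 84% |
| a quarter respond | 84% | 87% |
| none respond | 91% | 91% |

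Joint power can never exceed ITT-only power. It rises down the table because fixing the number of excluded non-responders also reduces the ITT variance. If that number varies by chance, the check run gives joint power of 78%, 80% and 82%, against 84% for ITT alone.

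**The case against.** The strongest reply has four parts.

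- **Redaction.** The text after the EMA rule in protocol 9.4.1.1 and most of SAP 4.10.2.2.3 to 4.10.2.2.8, including the EMA estimand table, is blacked out. A combination rule could sit there, so its absence from the visible text is no defect by itself. This stands. Such a rule would still sit against the visible supplementary label and would need a cross-reference.
- **Protocol 9.3.1.** The SAP follows one of two protocol sentences that do not agree. True, but 9.3.2 is the one specific to EMA, and the disagreement is a further reason to reconcile.
- **The PPS result will be reported anyway**, with the same methods and both intervals. True. Its part in the decision is what differs.
- **Both primary need not mean both must pass.** Correct. A reader might infer that the protocol sets a joint rule; the visible text does not say so, and every figure above depends on that assumption.

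A reader might also infer that everything about the PPS except its label is settled before unblinding. The documents do not support that. Membership is still to be determined (SAP 4.4.2). The requirement for at least one valid evaluation sits uneasily with a definition of validity that refers to all imaging at Weeks 12 and 28. SAP 4.10.2.3.2 runs two methods. Only the margin is fixed.

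**Conclusion.** The two documents give the PP population a different status in the EMA conclusion, in unredacted text, and the SAP does not declare the difference. That rests on wording alone and is wrong as written.

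The size of the consequence is conditional. It assumes a joint rule, 156 per arm, and exclusion rates and response rates that the visible documents mostly do not give. A reader might take 7 to 14% as the expected rate of conflicting results. That is the random-exclusion case at an assumed 75%; it is 1 to 3% at 88%, and lower where exclusions are mainly ITT non-responders. Likewise, the documents do not show that a joint rule would take power below the stated 80%. It may or may not, depending on the exclusion pattern and on planning inputs that are redacted.

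**What to change.** Before unblinding, do one of the following.

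**(a) Follow protocol 9.3.2.** State in SAP 4.10.2.1 that EMA equivalence requires the 95% CI within (-0.17, 0.17) in both ITT and PPS, by the exact score method in each. Move that part of 4.10.2.3.2 into the EMA main analysis. Qualify protocol 9.3.1 for EMA. Check joint power against the sponsor's own sample size re-estimation assumptions, and restate the 80% figure if it is not met, without changing N. Since the PPS would then carry a decision, clarify the valid-evaluation wording as well.

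**(b) If ITT alone is intended,** change protocol 9.3.2, and declare and justify the change in SAP 4.14.

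If a redacted passage already gives the rule, refer to it from SAP 4.10.2.1 and 4.10.2.3.2.

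**Cost.** Every analysis is already planned, so no new data or patients are needed. SAP changes are wording. Both routes also touch the protocol, whose section 10.1.10 says "To alter the protocol, amendments must be written, receive approval from the appropriate personnel, and receive IEC/IRB/Competent Authority approval prior to implementation". That section exempts administrative changes from formal amendment; the sponsor would have to justify using the exemption for a primary-population statement. The price of (a) is that joint EMA power cannot exceed ITT-only power and will usually be lower.
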